7.5. Pre-specified Subgroup Analysis

All subgroup analyses will be based on the ITT population, and presented as forest plots.

Subgroup analysis will be performed using the primary outcome as the dependent variable amongst patients with VAP caused by Gram-negative non-fermenters and carbapenem-resistant bacilli. Gram-negative non-fermenting bacilli include *Pseudomonas* spp., *Acinetobacter* spp., and *Stenotrophomonas* spp.. Carbapenem-resistant bacilli are Gram-negative bacteria which are resistant to at least one agent from the carbapenem category of antibiotics. VAPs caused by Gram-negative non-fermenters have been previously shown to be associated with increased recurrence^{12,13}. VAPs caused by carbapenem-resistant bacilli have no standardised treatment. This will be exploratory as the sample sizes for each of these groups will not reach adequate power.

Subgroup analysis will be performed with tests for interaction, where multivariable logistic regression models will be constructed with the occurrence of the primary endpoint as the outcome, and the randomised treatment as well as VAP caused by Gram-negative non-fermenters and carbapenem-resistant bacilli and the interaction between randomised treatment and pathogen type as explanatory variables. Odds ratio from the interaction tests will be presented with 95% CI and corresponding p-values.

For all pre-specified subgroup analyses, diagnostic checks will be performed as described in section 7.2.

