Because of the uncertainty about the exact causative organisms, ICUs are likely to utilise a high proportion of inappropriate empirical broad-spectrum antibiotics [17], which might contribute to the indirect ‘collateral damage’ of AMR emergence and dissemination to other patients. In Thailand, an alarming 95% of *A. baumannii* and 75% of *P. aeruginosa* isolates were recently found to be resistant to carbapenems, and 47% of *K. pneumoniae* isolates were ESBL-producing in VAP [18]. In Singapore, 91% of *A. baumannii* and 22% of all Gram-negative isolates collected during a 4-month period in 2010 were resistant to carbapenems in the “Comparative Activity of Carbapenem Testing” (COMPACT) study [19]. This emphasizes the importance of antimicrobial stewardship programmes (ASPs) which have shown to be capable of reducing broad-spectrum antibiotic consumption and potentially decreasing antibiotic resistance, particularly among Gram-negative pathogens [20-22]. However, current recommendations on ASP are based on very few conclusive studies as most ASP research was designed to evaluate cost-effectiveness instead of clinical outcomes such as reducing selection of MDR pathogens, mortality, hospital length of stay, and readmission rates [23-25]. In addition, operational delivery of ASPs is often hindered by cost, lack of diagnostics and data collection facilities, poor physician participation and lack of cooperative strategies [26]. Low uptake of ASPs, especially in SEA [27], calls for more rigorous and methodologically sound evaluations of ASP interventions to initiate practice and policy changes. Mathematical models offer tremendous potential for assessing the effectiveness of ASPs by removing the limitations inherent in human experimentation, including potential health risks, study cohort size and duration [28]. To date, the potential of modelling in evaluating ASPs in control of antimicrobial resistance is largely untapped and much work remains to be done to leverage this potential.

We aim to rationalise and reduce antibiotic consumption in ICUs and assess the benefit of this on both the individual patient and the overall cohort of ventilated patients. The specific aims are:

- i) to conduct a randomised controlled trial to assess the clinical efficacy of a short duration of antibiotics (up to 7 days) versus prolonged antibiotic therapy (physician preference) in adults patients with VAP ;

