4. OBJECTIVES AND OUTCOME MEASURES

Objectives	Outcome Measures	Timepoint(s) of evaluation of this outcome measure (if applicable)
Primary Objective To demonstrate clinical non-inferiority, followed by superiority, of a shorter antibiotic treatment duration compared to a longer duration in adult patients with VAP	Difference in the proportion of participants with the composite endpoint of death and VAP recurrence rate within 60(± 5) days of enrolment	All outcome measures will be assessed within day 60(± 5) of enrolment
Secondary Objectives To define other clinical benefits of shorter antibiotic treatment duration compared to a longer duration in adult patients with VAP	Ventilator-associated events, duration of mechanical ventilation, duration of hospitalisation, acquisition of multidrug resistant infection or colonisation during the hospitalisation, number of days of exposure to antibiotics during hospitalisation, number and types of extrapulmonary infections during hospitalisation (determined from cultures taken from sterile sites), difference in the proportion of participants with primary outcome in subgroups of patients with VAP caused by Gram-negative non-fermenters and carbapenem-resistant bacilli	All outcome measures will be assessed within day 60(± 5) of enrolment
To study the impact of various antibiotic regimen on the microbial community dynamics and diversity in the respiratory and intestinal tracts in individual patients in order to understand colonisation and transmission of MDROs, identify potentially protective components of the microbiome against MDROs	Characteristics of the microbiota will be determined by comparing alpha and beta diversity metrics between the groups of patients, alterations in the repertoire of antibiotic resistant genes, shifts in microbiota functional and metabolic capacity	Respiratory and stool samples will be collected from the study participants within 24 hours of enrolment, weekly during hospitalisation, and at day 28 (± 5) and 60(± 5) after enrolment

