5. STUDY DESIGN

The study design is a randomised, partially double-blinded (blinding may be achieved up to 7 days) controlled trial to assess the efficacy of short vs. longer antibiotics course in adults with VAP. The trial has a stepwise noninferiority–superiority hypothesis, i.e., if non-inferiority of short duration, compared with long duration, is shown, statistical tests for superiority will be performed using closed testing methods without requiring adjustment of the significance level for multiple comparisons.

Screening and inclusion criteria

We will apply the US Centers for Disease Control and Prevention (CDC) National Healthcare Safety Network (NHSN) VAP diagnostic criteria on patients who have been mechanically ventilated for ≥ 48 hours as our

study subject inclusion criteria [29]. While we acknowledge that there is no “gold standard” diagnostic criteria to VAP and that clinical criteria correlate poorly with autopsy findings (previously determined to be 69 % sensitivity and 75 % specificity [30]), the CDC NHSN diagnostic criteria is sensitive and practical for use in ICUs of various resources and settings. Only one episode of suspected VAP will be included for this study.

We agree with the 2016 Clinical Practice Guidelines by the Infectious Diseases Society of America (IDSA) and the American Thoracic Society (ATS) guideline that the additional use of infection scores and other biomarkers including procalcitonin, c-reactive protein, and soluble triggering receptor expressed on myeloid cells-1 lack sensitivity and specificity and will not be included in our inclusion criteria [3].

Microbiological culture results are not part of our inclusion criteria so that we are able to recruit patients who have suspected VAP but respiratory cultures are negative. Management strategies for this group of patients have not been defined by a randomised study. There are two observational studies that compared outcomes among those whose antibiotics were withheld on the basis of negative respiratory cultures to those whose antibiotics were continued [32, 33]. Patients whose antibiotics were discontinued did not have a higher mortality or rate of new respiratory infection compared to patients whose antibiotics were continued.

Randomisation and Intervention

Following screening and fulfilling the inclusion/exclusion criteria, the study subject will be recruited within 72 hours. Antibiotic treatment course will be determined according to randomisation.

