This is a non-inferiority trial with a hierarchical noninferiority–superiority hypothesis. The first analysis to be conducted will be for determination of non-inferiority. Only if non-inferiority is established by this primary analysis, a second analysis for superiority will be conducted using closed testing methods without requiring adjustment of the significance level for multiple comparisons. [39] The trial estimates for the primary outcome will be calculated with the absolute risk difference (proportion of participants with the primary outcome in the short arm minus that in the long arm). Hence, non-inferiority will be concluded if the upper boundaries of the one-sided 95% confidence intervals from both unadjusted and adjusted analyses are below the non-inferiority margin. The purpose of using both adjusted analyses on the intention-to-treat and per-protocol populations to determine non-inferiority is to minimise the inflation of type 1 error associated with non-adherence in non-inferiority trials. [40] Superiority will be declared if the entire confidence intervals for all the trial estimates are above zero.

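### The SAP drops the subgroup risk difference that the protocol lists as an outcome and names only an interaction odds ratio, which cannot be read against the absolute 12% margin

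*SAP*

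**What the plan says.** - **Protocol, Synopsis and section 4.** The secondary outcomes include the "difference in the proportion of participants with primary outcome in subgroups of patients with VAP caused by Gram-negative non-fermenters and carbapenem-resistant bacilli". That is an absolute contrast.
- **Protocol 10.1.** The primary effect is on the same scale: "The trial estimates for the primary outcome will be calculated with the absolute risk difference". The margin in SAP 2.5 is likewise 12 percentage points, absolute.
- **SAP 2.1 and 2.6.** Secondary endpoints (a) to (g) are listed with definitions and hypotheses. The subgroup difference is not among them.
- **SAP 7.5.** The primary outcome will be analysed among patients with these pathogens. On population and display: "All subgroup analyses will be based on the ITT population, and presented as forest plots". The logistic models contain treatment, pathogen, and "the interaction between randomised treatment and pathogen type as explanatory variables". The stated output is: "Odds ratio from the interaction tests will be presented with 95% CI and corresponding p-values". Section 7.2 is cited only for diagnostic checks.
- **Status.** SAP 7.5 is open about precision: "This will be exploratory as the sample sizes for each of these groups will not reach adequate power". Protocol 10.1 says the same.

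**The concern.** An outcome that the protocol lists as a difference in proportions has no estimate assigned to it in the SAP. The one statistic that is named is on a different scale from the outcome, the primary effect and the margin. It also answers a different question: whether the odds ratio differs between groups, not how large the excess is within a group.

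This matters because the protocol's background says the earlier short-course trials could not be applied with confidence to non-fermenters, and that most VAP in the region is caused by them. Readers will look for this result. With only an interaction odds ratio and a p-value, they could not tell whether the data in non-fermenters are compatible with an excess of 12 points.

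There is also an ambiguity in the model. Carbapenem resistance is defined in SAP 7.5 without excluding non-fermenters, so one patient can belong to both groups, and the SAP does not say whether the two factors share a model.

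**Working it through.** **Inputs from the documents.** Event rate 55%, margin 12 points, one-sided 5%, 80% power, 412 evaluable, 460 enrolled (SAP 2.5); 1:1 allocation (SAP 2.4); 0.05 for additional analyses (SAP 7.3), taken here as two-sided.

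**Assumption.** The documents say that non-fermenters are the majority but give no share. I use 60% and show 50% to 80%.

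**1. The plan's own figure.** The formula is not named. With z = 1.645 and 0.842:
- 55% v 67%, pooled variance: 408
- 55% v 67%, unpooled: 404
- 55% in both arms with a 12-point margin: 426

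The first two are within 3% of 412, before any group-sequential allowance. 412/0.9 = 458, consistent with 460. No sample size or power is stated for the subgroups.

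**2. Scale.** Take 70% v 55%: OR = (0.70/0.30)/(0.55/0.45) = 1.91. Apply the same OR at other control risks:

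| Control risk | Short-arm risk | Excess |
|---|---|---|
| 45% | 61% | 16 points |
| 55% | 70% | 15 points |
| 65% | 78% | 13 points |

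If a pathogen group and its complement had any two of these control risks, the interaction odds ratio would be exactly 1 while both groups exceeded 12 points.

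**3. Precision of the risk difference in the subgroup.** 412 × 0.60 = 247.2 patients, 123.6 per arm.
- SE = sqrt(2 × 0.55 × 0.45 / 123.6) = 0.0633
- 90% CI half-width = 1.645 × 0.0633 = 10.4 points; 95% CI half-width = 1.96 × 0.0633 = 12.4 points
- Chance that the upper 90% limit is below 12 points if the true difference is zero: Φ(0.12/0.0633 − 1.645) = Φ(0.25) = 60%

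| Share | 90% half-width | Chance |
|---|---|---|
| 50% | 11.4 | 53% |
| 60% | 10.4 | 60% |
| 70% | 9.6 | 66% |
| 80% | 9.0 | 71% |

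**4. Power of the interaction test.** Risk is 67% in the short arm of the subgroup and 55% elsewhere; 82.4 per arm in the complement.
- Log-odds scale: ln(1.66) = 0.508. Variance = 1/(123.6 × 0.2475) + 1/(123.6 × 0.2211) + 2/(82.4 × 0.2475) = 0.167, SE = 0.409, z = 1.24, power 24%.
- Risk-difference scale: SE = sqrt(2 × 0.2475/123.6 + 2 × 0.2475/82.4) = 0.100, z = 1.20, power 22%.

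The two scales agree closely, so the low power comes from the sample size and not from the odds ratio. For shares of 50% to 80%, the log-odds figure is 24% to 17%. For a 20-point excess it is 59% to 43%.

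**5. Overlap.** Protocol section 3 reports that in Thailand 95% of *A. baumannii* and 75% of *P. aeruginosa* "isolates were recently found to be resistant to carbapenems". Assume 60% non-fermenters, 75% to 95% of them resistant, and 10% to 20% resistance among the rest (this last range is in neither document). The correlation φ of the two indicators is then 0.54 to 0.85. If both interactions sit in one model, each variance is multiplied by roughly 1/(1 − φ²) = 1.4 to 3.7, and each SE by about 1.2 to 1.9.

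**The case against.** The case on the other side is substantial.

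- **Silence is not exclusion.** SAP 7.5 promises analysis within the pathogen groups and forest plots, which would normally show within-group effects. SAP 7.2 already uses logistic regression to obtain treatment differences, so the model type does not rule out risk differences. This stands: a reader might infer that the sponsor chose the odds ratio instead of the absolute difference, and the text does not go that far. What remains is that nothing commits the sponsor to the listed estimate. SAP 8.1 repeats the 7.2 analysis for secondary outcomes, but these are the ones defined in 2.6, where this outcome is missing.
- **One model or two.** SAP 7.5 speaks of models in the plural and of pathogen type in the singular. A joint model is one reading only, so the inflated standard errors are conditional on it.
- **Power.** A reader might infer that the test could not detect a problem. That is too strong, given 43% to 59% power for a 20-point excess. Nor should the interaction power be set against the chance of excluding 12 points: one is about detecting an excess, the other about ruling one out when none exists.
- **Disclosure.** Both documents label the analysis exploratory and underpowered. That answers a complaint about power. It does not supply the missing estimate or scale.
- **Culture-negative patients.** Protocol section 5 recruits them deliberately and says: "Management strategies for this group of patients have not been defined by a randomised study". A reader might infer that they need their own level in the model. No document lists them as a subgroup, and the protocol's background itself warns about excessive subgroup analysis, so this is a preference and not a defect.

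**Conclusion.** The point holds as a loss between protocol and SAP. A listed secondary outcome, the absolute difference within two pathogen groups, is absent from the SAP's secondary endpoints, and the only subgroup statistic named cannot be compared with the 12% margin. This rests on the text and on the algebra of odds ratios, not on any assumed prevalence.

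The sizes do rest on assumptions. With 412 evaluable, 55% events and 60% non-fermenters, a 90% interval of about ±10.4 points is informative but not decisive. The overlap figures rest on resistance rates from outside the trial and apply only if both factors share a model.

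The gain is in readability against the margin. The subgroup result would still fall short of 80% power, and the documents do not offer it as confirmatory.

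**What to change.** In SAP 7.5, state that:

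1. the short-minus-long risk difference in the primary outcome, with 90% and 95% CI, is reported for each pathogen group and its complement in the ITT population;
2. the forest plot uses the risk-difference scale;
3. each pathogen factor is fitted in its own model, or the two are recoded into mutually exclusive categories, with the choice fixed before analysis;
4. the interaction test is kept as supportive;
5. all of this remains exploratory.

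A one-line pointer from SAP 2.6 would show where the protocol's listed outcome is handled. The cost is a few lines of SAP text and code and a redrawn plot. No new data, patients or change to the primary analysis are needed.

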7.6. Treatment by Centre Interaction

Consistency of potential effects will be assessed across all centres by informal examination of the within-centre effects. There will be limited capacity to investigate these formally due to small sample sizes. Treatment allocation by centre interaction will be explored and treatment effects will be presented as forest plots without the performance of statistical tests. This summary will only include centres where patients were randomised in both arms.

7.7. Sensitivity Analysis

No sensitivity analysis in addition to that discussed in the above sections is planned in the context of the primary analysis. The above-described analyses (including both the ITT and PP analysis, which are parts of the primary analysis described above) are sufficient to assess the robustness of the trial results.

8. ANALYSES TO ADDRESS SECONDARY AIMS

Secondary outcomes are defined in section 2.6.

8.1. Statistical Methods Used for Analysis of Secondary Outcomes

The primary analyses described in section 7.2 will be repeated for secondary outcomes, based on the ITT population. Similar analysis on the PP population will be included in the supplementary materials.

8.2. Ventilator-Associated Events

Episodes of ventilator-associated events will be summarised overall and by treatment arm (frequency and percentages). Participants will be categorised as either having or not having experienced ventilator-associated events. Using this as a binary outcome variable, the analysis described in section 7.2 will be repeated.

8.3. Adverse Events and Complications

Episodes of antibiotic-related diarrhoea, allergy reactions and other side effects, readmissions will be summarised overall and by treatment arm (frequency and percentages). Participants will be categorised as either having or not having experienced adverse events. Using this as a binary outcome variable, the analysis described in section 7.2 will be repeated.

A breakdown of serious adverse events (SAE) will also be presented in this section. SAEs in REGARD-VAP trial include deaths and pneumonia recurrences, which already contribute to the primary outcome. In a detailed breakdown of these SAEs, the number of participants with at least one recorded SAE, as well as the number of SAE reported per participant will be included. In addition, summaries will include the timing of the report from randomisation and whether complications were expected and / or thought to be related to the randomisation, and the outcome of any SAEs will be summarised.

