Persistent VAP or treatment failure is defined as the lack of improvement of hemodynamic stability or ventilation requirements without an alternative cause other than the same episode of VAP. These patients will be continued to be monitored for the above-described “fitness criteria” and antibiotics should be stopped when they eventually meet the criteria. Recurrent VAP is defined as an additional episode of VAP satisfying the CDC clinical and radiological criteria of VAP [29] following commencement of the primary VAP treatment within 60(+5) days of enrolment. Opinion from 2 respiratory experts blinded to the randomisation will be sought to diagnose persistence and recurrences. Patients who are diagnosed with an alternative source of infection or a complication from VAP such as lung abscess or empyema that warrant a duration of antibiotics longer than 7 days prior to the last day of assigned duration of antibiotics are not considered treatment failures. These patients will not meet fitness criteria for randomisation and be discontinued from the study and subsequent analysis (see section 7.8). In cases where patients randomised to short duration and satisfy the above-described “stop criteria” but did not have their antibiotics stopped by day 7, they are considered protocol deviations. They will be analysed with intention to treat analysis.

Duration of antibiotics in control group will be at least 8 days with the exact duration decided by the managing physicians.

Adverse events will be recorded throughout the study period, including *C. difficile* infection, acute kidney injury, hepatitis, drug allergies, haematological and other complications.

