2. BACKGROUND INFORMATION

2.1. Objectives

Primary objective

To assess the effect of short (7 days or fewer depending on clinical response) versus long (8 days or more depending on physicians' preference) antibiotic treatment strategies on mortality and pneumonia recurrence within 60 days of enrolment in adults with ventilator-associated pneumonia (VAP) in Asia.

Secondary objectives

To compare the following endpoints according to treatment allocation within 60 days of enrolment:

- a) Ventilator-associated events
- b) Duration of mechanical ventilation
- c) Duration of hospitalisation
- d) Acquisition of multidrug resistant infection or colonisation during the hospitalisation
- e) Number of days of exposure to antibiotics during hospitalisation
- f) Number and types of extrapulmonary infections during hospitalisation (determined from cultures taken from sterile sites)
- g) Adverse events, i.e. antibiotic related diarrhoea, allergic reactions, readmissions

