H_0 : There is no difference in the number of sterile site infections in the short and long treatment strategy groups, i.e. $x_s = x_l$;

H_1 : There is a difference in the number of sterile site infections in the short and long treatment strategy groups, i.e. $x_s \neq x_l$;

where x_s is the number of sterile site infections in the short and x_l is the number of sterile site infections in the long treatment strategy groups.

g) Adverse events, i.e. antibiotic related diarrhoea, allergic reactions

Definition: Number and types of adverse events during 60 days of follow-up, which include antibiotic related diarrhoea, allergic reactions, readmissions

H_0 : There is no difference in the number of adverse events in the short and long treatment strategy groups, i.e. $x^{AE}_s = x^{AE}_l$;

H_1 : There is a difference in the number of adverse events in the short and long treatment strategy groups, i.e. $x^{AE}_s \neq x^{AE}_l$;

where x^{AE}_s is the number of adverse events in the short and x^{AE}_l is the number of adverse events in the long treatment strategy groups.

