2.7. Outcomes Assessment Schedule

Baseline assessments are performed prior to randomisation on day 0. Other important assessment time points are detailed below.

Time point (Day)	Activity
0	Enrolment, baseline assessments.
Antibiotic prescription	
0-7	Antibiotic choice(s) is / are checked against respiratory endotracheal tube cultures. If current antibiotic choice(s) is / are not appropriate, primary physicians are advised to switch antibiotic choice according

	
to antibiotic susceptibility report (when there is positive growth) or local microbiology antibiogram (when there is no positive growth).
 
Randomisation to short or long treatment strategy. If randomisation is to short arm, all antibiotics for the participant should be stopped on the day of randomisation (other than, when applicable, anti-tuberculosis antibiotics, prophylaxis e.g. peri or post operative or in immunocompromised hosts, gut prokinetic antibiotics)

0 - discharge	Weekly follow-up for new or changes in antibiotic prescription for all participants.
Outcome assessment	
0 - discharge	
New or changes in antibiotic prescription or new respiratory culture reports will trigger screening for pneumonia recurrence. The US CDC VAP diagnostic criteria will be checked during the preceding week.
 
When these diagnostic criteria are met, two independent respiratory or infectious diseases physicians who are blinded to the randomisation arm will be consulted to verify if the episode is a recurrent episode.

0 - 60	
Mortality is assessed weekly.
 
Secondary outcomes such as adverse events, discharge / readmissions, intubation / extubation, clinical cultures, biochemistry laboratory tests are recorded weekly.

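### The tested adverse-event variable combines drug reactions with readmission, so the comparison is diluted and depends on survival and length of stay

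*SAP*

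**What the plan says.** SAP 2.1(g) lists the secondary endpoint as "Adverse events, i.e. antibiotic related diarrhoea, allergic reactions, readmissions". The definition in SAP 2.6(g) again puts readmission inside it ("which include antibiotic related diarrhoea, allergic reactions, readmissions"), although the heading of that item leaves readmission out. The null hypothesis there concerns a count: "There is no difference in the number of adverse events in the short and long treatment strategy groups".

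SAP 8.3 does two things. It tabulates episodes of diarrhoea, allergy, other side effects and readmission by arm. It then reduces them to one variable, "Participants will be categorised as either having or not having experienced adverse events", and applies the section 7.2 analysis to it. No rule is given for patients who die before discharge.

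On timing, SAP 2.1 sets the comparison within 60 days of enrolment, and SAP 2.7 places randomisation between day 0 and day 7. SAP 8.8 limits bloodstream infections to those after randomisation; SAP 8.3 has no such limit.

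On blinding, SAP 2.4 keeps patients blinded but unblinds the investigator, who then contacts the physicians, once the stopping conditions are met. SAP 5.7 accepts that treating physicians cannot be fully blinded. Blinded experts judge VAP recurrence and persistence; none are described for adverse events.

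Protocol 8 records a wider list of events, "including *C. difficile* infection, acute kidney injury, hepatitis, drug allergies, haematological and other complications". SAP 2.4 repeats that list and adds readmissions.

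**The concern.** Readmission and a drug reaction are different kinds of event. A reaction can occur in any patient on treatment. Readmission can occur only in a patient who leaves hospital alive before day 60. In a population where the plan expects death or recurrence in 55%, many patients may never be at risk of it. On the plain wording of 8.3, someone who dies in the ICU with no reaction counts as free of adverse events. An arm with better survival or earlier discharge gains events, and an arm with more early deaths loses them.

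Two smaller problems point at the same variable. Reactions between enrolment and randomisation cannot result from the allocation, yet they count. And whether diarrhoea is antibiotic-related may be judged by staff who know whether the patient is still on antibiotics.

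At stake is how one secondary result is read. If non-inferiority is shown, readers will look at adverse events for a further benefit of the shorter course, and the single tested number does not isolate that.

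**Working it through.** The documents state no adverse-event, readmission or discharge rate, and no power for this endpoint, so there is no figure to reproduce. All rates below are assumptions.

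**Inputs**
- From the SAP: 230 per arm (2.2); two-sided tests for secondary endpoints (2.6); significance level 0.05 (7.3).
- Assumed: drug-reaction risk *d* of 20% long v 12% short, or 15% in both arms; share discharged alive *a* of 50 to 70%; readmission risk among those discharged *r* of 10 to 30%; reactions and readmission independent.

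**Formula.** Risk of any event in an arm = 1 − (1 − *d*)(1 − *a·r*). Two consequences follow:
- If *a·r* is the same in both arms, the difference is (d_long − d_short)(1 − *a·r*), which is always smaller than the true difference.
- If *d* is the same in both arms, short minus long is (1 − *d*)·*r*·(a_short − a_long). This is not zero, and its sign follows discharge alive rather than toxicity.

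**1. Dilution, same discharge in both arms, 20% v 12%**
- *r* = 10%, *a* = 50%: 1 − 0.80×0.95 = 24.0%; 1 − 0.88×0.95 = 16.4%; difference 7.6 points.
- *r* = 30%, *a* = 70%: 1 − 0.80×0.79 = 36.8%; 1 − 0.88×0.79 = 30.5%; difference 6.3 points.
- Power = Φ{[Δ − 1.96√(2p̄(1−p̄)/230)] / √((p₁q₁+p₂q₂)/230)}. This gives 65% for drug reactions alone, 53% in the first case and 30% in the second.

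**2. Survival dependence, equal toxicity of 15%**
- *r* = 10%, discharged alive 55% short v 50% long: 0.85×0.10×0.05 = 0.4 points.
- *r* = 30%, 60% v 50%: 0.85×0.30×0.10 = 2.55, about 2.6 points.
- The short arm looks worse although toxicity is equal. If the long arm discharged more patients alive, the sign would reverse.

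**3. Both together: 12% short v 20% long, discharged alive 60% v 50%**
- *r* = 10%: 1 − 0.88×0.94 = 17.3%; 1 − 0.80×0.95 = 24.0%; difference 6.7 points.
- *r* = 30%: 1 − 0.88×0.82 = 27.8%; 1 − 0.80×0.85 = 32.0%; difference 4.2 points.
- The true difference is 8.0, so 1.3 to 3.8 points are lost.

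**4. Attribution, equal true risk of 15%.** Suppose 90% of events are labelled antibiotic-related in the long arm and 80% in the short arm: 0.15×(0.90 − 0.80) = 1.5 points of false benefit. With 60% in the short arm: 0.15×0.30 = 4.5 points. This treats the whole 15% as subject to the label. Since the label attaches to diarrhoea only, the effect shrinks in proportion to diarrhoea's share of events.

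**5. Window.** If a share *e* of each arm has a reaction before randomisation, independent of later ones, the difference is multiplied by (1 − *e*). That dilutes the contrast without biasing it. The documents give no value for *e*.

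**The case against.** The strongest reply is that 8.3 also tabulates the components by arm and presents a breakdown of serious events, deaths included. Drug reactions can thus be read apart from readmission, and a high-mortality arm could not quietly pass as safer. That stands against any inference that the plan cannot show toxicity at all. It does not remove the point, because the estimate, interval and test attach only to the combined variable.

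Several stronger readings are tempting, and the documents do not support them:
- *That the trial is open-label.* It is described as partially double-blinded, with patients blinded. Only staff knowledge after the stop point is at issue.
- *That all reactions depend on local attribution.* The wording is tied to diarrhoea, not to allergy or other side effects, and the documents do not say who makes the judgement. Short-arm patients may also restart antibiotics (SAP 5.5).
- *That kidney, liver, haematological and C. difficile events are excluded.* The list in 2.6(g) is not closed, 8.3 adds other side effects, and SAP 2.4 names these events. The scope is unclear rather than narrow.
- *That half the benefit would vanish.* With toxicity 15% v 25% and readmission 25%, discharge alive of 60% v 40% gives 27.8% v 32.5%, or 4.8 points of a true 10. That needs a 20-point gap in discharge alive. At 55% v 45% the difference is 6.8 points, and with no gap (50% in both) it is 8.8.
- *That the endpoint should be rebuilt from laboratory values.* SAP 2.7 says "clinical cultures, biochemistry laboratory tests are recorded weekly", but Protocol 7.5 describes baseline tests as routine ones ordered by the clinical teams. Appendix B schedules no blood test at day 28 or 60, and follow-up may be by telephone (Protocol 7.6). Laboratory detection would depend largely on being alive and in hospital, which is the same weakness.

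It is also fair that reducing antibiotic consumption and resistance is the trial's stated rationale. Those have their own endpoints, and adverse events are not in the protocol's list of secondary outcomes. This limits the importance of the point.

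**Conclusion.** The point holds in a limited form. The tested variable mixes drug reactions with an event that needs discharge alive, no rule covers death in hospital, and the window includes time before randomisation. The comparison is therefore diluted and depends on survival and stay. Unblinded labelling of diarrhoea could add a bias in the other direction.

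The size is unknown. Under the assumed rates, with gaps in discharge alive of no more than 10 points, it is a few percentage points at most: 0.4 to 2.6 points of false difference, or 1.3 to 3.8 points lost from a true 8. These figures rest on independence of reactions and readmission and on rates the documents do not supply. Separately, 2.6(g) states a hypothesis on the number of events while 8.3 tests yes/no; the two need to agree. This concerns a secondary endpoint and leaves the non-inferiority decision untouched.

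**What to change.** In SAP 2.6(g) and 8.3:

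1. Apply the binary analysis to drug-related adverse events with onset after randomisation. Use the list already recorded under Protocol 8 and SAP 2.4 without readmission, together with the diarrhoea that 2.6(g) already names.
2. Analyse readmission as a separate outcome over all randomised patients, show the number discharged alive in each arm, and treat death before discharge as a competing event.
3. Report diarrhoea regardless of attributed cause beside the attributed count, where it is recorded.
4. Make the 2.6(g) hypothesis and the 8.3 analysis address the same quantity, whether number of events or any event.

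The cost is SAP wording and re-derivation. SAP 2.7 records adverse events, discharge, readmission and mortality weekly, and SAP 3 plans a full check of randomisation, discharge and readmission dates. Protocol Appendix B schedules daily adverse-event assessment in hospital, so onset can be placed relative to randomisation provided the case report form holds the date. The downside is one more secondary comparison and fewer events in the drug-reaction variable.
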